18.1. Interim analyses for the IDMC

The POC Trial as such will not control for the Type I error. For each IST, the sample size and the stopping criteria are set in consideration of the Type I error, which is evaluated by simulation.

The interim analyses will be conducted every three months. It will be the same time for all ISTs, but the analyses will be made separately. The actual analysis will follow the principles for the primary efficacy analysis described in Section 14.

For each evolution analysis conducted in which an intervention has reached a minimum exposure to research participants, an analysis of graduation (success) will be conducted. With the same constraints, an analysis of futility will be conducted. The default criterion is at least 50 research participants with 12 months of follow up in an intervention cohort, but this can be specified within an ISA. The details of these analyses are:

1. If the posterior probability of a $CPRR < 0.90$ is greater than 0.85 then the intervention meets graduation criteria and will be labelled a success. This analysis concludes a super superiority, meaning there is high probability of at least a 10% slowing in the rate of decline is met for the intervention
2. If the posterior probability of a $CPRR < 0.90$ is less than 0.05 then the futility criteria is met for that intervention. Thus, if there is high probability of less than a 10% slowing in the rate of decline, the intervention will be declared futile.

The sponsor will only be informed of the decision to continue or stop the trial and will not be unblinded to the results until the study has ended.

18.2. Interim analyses for the DSMB

This section is not finalized.

19. Sample size considerations

The maximum exposure for a research participant to an intervention is 4 years. The time of follow-up (a maximum of 4 years) and maximum number of research participants enrolled to an intervention cohort is defined in the ISA. Complete power calculations and operating characteristics for each intervention will be detailed in the ISA.

A suggestion for a general strategy for power calculations for some generic possible choices of number of subjects, subgroups, and length of follow-up is given in the master protocol.

 EPAD - 115736	D2.11 Master Statistical Analysis Plan for the EPAD Platform Proof-of-Concept Trial		
	WP2. Statistical/Methodology Engine Room	Version: v2.0 – Final	
	Author(s): [name], [name], [name]	Security: PU	32/36

20. Statistical software

Final study reports will be generated using SAS version 9.4 or later. The efficacy models described in this master SAP will be coded in C++ version XXX or later. The ISA will specify further software used for a specific sub trial.

Appendix I gives example SAS code to fit a simplified version of the primary analysis.

21. Changes to analyses specified in the protocol

There are no changes to analyses specified in the protocol.

22. Details on data handling

Details on data handling will be specified in the ISA.

23. Transfer of data from LCS

Transfer of data from LCS has two purposes. One is avoiding screening assessments, when a similar assessment has been done shortly before. The other point is that the primary endpoint analysis includes data from the LCS as reflection of the status and development of the research participant during their time in the LCS.

At the screening visit (V1), some assessments performed in the LCS within the past 3 to 12 months prior to the screening visit of the PoC trial will be considered acceptable and will not be necessarily re-assessed:

- If the PoC screening visit is performed the same day or within (\leq) 3 months of a LCS visit, then the clinical outcome assessments that are the same in both studies will be performed only once
- If the PoC screening visit is performed more than ($>$) 3 months after a LCS visit, then the clinical outcome assessments will need to be re-performed.

At screening Visit 2, in order to reduce invasive assessments, repetition of examinations and subject burden, the following existing data performed in the LCS within pre-defined time intervals may be eligible:

- Secondary and exploratory clinical outcome assessments within the past 3 months prior to V1
- Lumbar puncture for CSF sampling done in the LCS within past 12 months prior to V1
- MRI performed in the LCS within past 6 months prior to V1.

24. Communication of results

Sharing of placebo data will be conducted between each study cohort. Research participants, Investigators and everyone involved in the conduct or analysis or with any other interest in this trial conduct will not be blinded across different intervention cohorts but will remain blinded with regard

 EPAD - 115736	D2.11 Master Statistical Analysis Plan for the EPAD Platform Proof-of-Concept Trial		
	WP2. Statistical/Methodology Engine Room	Version: v2.0 – Final	
	Author(s): [name], [name], [name]	Security: PU	33/36

to the randomized treatment arm assignments within their intervention cohort until after database lock.

The randomization code will be kept secret and only accessed by the External Statistical Clinical Research Organisation (CRO) and the Independent Data Monitoring Committee (IDMC), until an intervention completes its exposure in the trial.

The Sponsor and the External Statistical CRO will have access to unblinded data as the trial evolves. The Sponsor, External Statistical CRO, and the IDMC will follow detailed procedures in order to avoid unnecessary unblinding of any individual research participants or unblinding of ongoing combined trial results

On completion of the study, the study data will be analysed and tabulated, and a clinical study report will be prepared in accordance with ICH guidelines. Publications will be generated from the intervention specific appendices and their management will be articulated in the intervention specific appendices.

When a report on one IST using controls from other ISTs, there is a risk of indirect unblinding of individual subjects in those other ISTs, for example, due to presence or absence of specific rare adverse events, which combined with blinded information from the other ISTs can lead to certain or probable treatment classification. Before release of a report, this problem will be considered, potentially leading to blinding of selected details in the report before release.

25. References

Randolph C, Tierney MC, Mohr E, Chase TN. The Repeatable Battery for the Assessment of Neuropsychological Status (RBANS): Preliminary Clinical Validity. *Journal of Clinical and Experimental Neuropsychology*. 1998b;20(3):310-319.

 EPAD - 115736	D2.11 Master Statistical Analysis Plan for the EPAD Platform Proof-of-Concept Trial		
	WP2. Statistical/Methodology Engine Room	Version: v2.0 – Final	
	Author(s): [name], [name], [name]	Security: PU	34/36

PUBLIC SUMMARY¹

The purpose of the EPAD Proof-of-concept (PoC) Platform Trial Protocol is to study multiple interventions for the secondary prevention of Alzheimer’s dementia in people with prodromal or preclinical Alzheimer’s disease. This document is the corresponding Statistical Analysis Plan (SAP). As the PoC Platform Trial was not initiated, the SAP has not been finalized. The role of this document is to make the material available for future use. Consequently, it has not been a priority to make the document have a finished appearance. In other words, the document includes unfinished parts.

As a master SAP, a key point is to describe the data sharing between the Intervention-specific trials and the consequences of this sharing. A second point is to describe the common methods, in particular, the interim analyses used to decide on whether the trials stop or continue. Each Intervention Specific Trial will have a dedicated SAP.

Each intervention specific trial will have interim analyses for efficacy made every 3 months, after 50 research participants have reached 12 months of follow-up. The primary endpoint is RBANS total score. The dataset for the analysis consists of all available data for the research participants in the intervention specific trial supplemented with placebo data from the other intervention specific trials within the relevant strata. The model is a Bayesian disease progression model, where the placebo group has an arbitrary development over time, in each of the up to four strata recruiting to the trial. The active treatment group is assumed to show a change from baseline multiplied by a common factor (CPRR: Cognitive Progression Rate Ratio), so a value below 1 means that the disease progression is delayed. If an interim analysis shows that the posterior probability of $CPRR < 0.90$ is greater than 0.85, the intervention meets the success criterion. If the posterior probability of $CPRR < 0.90$ is less than 0.05, the intervention is declared futile.

¹ This summary will be published on the EPAD website in case the Executive Summary cannot be published. In case the Executive Summary can be made publically available, you can simply copy/paste for the Public Summary

 EPAD - 115736	D2.11 Master Statistical Analysis Plan for the EPAD Platform Proof-of-Concept Trial		
	WP2. Statistical/Methodology Engine Room	Version: v2.0 – Final	
	Author(s): [name], [name], [name]	Security: PU	35/36

ANNEXES

 EPAD - 115736	D2.11 Master Statistical Analysis Plan for the EPAD Platform Proof-of-Concept Trial		
	WP2. Statistical/Methodology Engine Room	Version: v2.0 – Final	
	Author(s): [name], [name], [name]	Security: PU	36/36

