- Additional arguments amongst those stated before, like alternative explanation (e.g., situations where other drugs or underlying diseases appear to provide a more likely explanation for the observed event than the drug concerned).
 - Disappearance of the event even though the intervention continues or remains unchanged.

16. Pharmacokinetic/Pharmacodynamic analyses

No PK assessments are required in the Master Protocol. If any specific assessments are required for an intervention, they will be articulated in the Intervention Specific Appendix of the Master Protocol and relevant statistical analyses will be described in the ISA of the master SAP.

17. Data monitoring committees

An IDMC, and a separate Data Safety Monitoring Board (DSMB), both independent of the Sponsor and the Intervention Owners, will be established to assess the progress of the clinical trial, including unblinded safety (DSMB) and efficacy (IDMC) assessment at specified intervals, and to recommend to the PSC and ASC whether to continue, modify, or stop interventions within the trial. Measures are in

 EPAD - 115736	D2.11 Master Statistical Analysis Plan for the EPAD Platform Proof-of-Concept Trial		
	WP2. Statistical/Methodology Engine Room	Version: v2.0 – Final	
	Author(s): [name], [name], [name]	Security: PU	31/36

place to ensure confidentiality and blinding of the Sponsor and all other trial participants. The tasks and responsibilities of the IDMC and DSMB will be specified in IDMC and DSMB Charters, respectively. The IDMC and DSMB will maintain written records of all their meetings.

18. Interim analyses

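### Section 24 gives the Sponsor unblinded data while the trial runs; Sections 17 and 18.1, and Section 24's own limit on the randomization code, say the opposite

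*Combined protocol and SAP*

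**What the plan says.** Four places in the SAP bear on what the Sponsor may see while an IST is running.

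- **Section 17 (Data monitoring committees)** assigns unblinded efficacy review to the IDMC and unblinded safety review to the DSMB. It says measures exist to "ensure confidentiality and blinding of the Sponsor and all other trial participants".
- **Section 18.1 (Interim analyses for the IDMC):** "The sponsor will only be informed of the decision to continue or stop the trial", and the sponsor "will not be unblinded to the results until the study has ended".
- **Section 24 (Communication of results), opening:** all those involved in conduct or analysis know which IST a participant is in, but stay blinded to the arm within it until the database is locked.
- **Section 24, second paragraph:** the randomization code is secret and open only to the External Statistical CRO and the IDMC "until an intervention completes its exposure in the trial". The next sentence reads: "The Sponsor and the External Statistical CRO will have access to unblinded data as the trial evolves". A third sentence commits the Sponsor, the CRO and the IDMC to procedures against needless unblinding of individuals and against unblinding of combined results still in progress.

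**The concern.** Section 5 describes a double-blind trial, and Section 18.1 provides for quarterly analyses with success and futility rules. In such a design the people running the trial should not see comparative data while decisions remain open. The SAP leaves at least two such decisions until late and asks that they be made blind.

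- **Analysis-set classification.** Section 8.4 has participants and data classified at a meeting after the database is released and before the blind is broken.
- **The all-controls cut-off.** Section 8.2 requires the last enrolment date for that set to be fixed before unblinding. The choice could touch the main result, because item 1 of the analysis list in Section 14 makes the all-controls set primary. (Section 8 names concurrent controls instead, which is a separate inconsistency.)

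If the Sponsor already holds unblinded data, neither step can be shown to have been taken independently of the results. The SAP is published for future use, so anyone adapting it would inherit a sentence that permits what other sections forbid.

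**Working it through.** No arithmetic applies. The check sets the statements side by side and asks whether any reading satisfies them all.

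1. **Same party?** Section 17 and Section 24 both use the capitalised term Sponsor, and Section 17 distinguishes the Sponsor from the Intervention Owners. A change of party therefore does not explain the clash between those two sections. Section 18.1 uses lower case, so the party there is slightly less certain. The conflict with Section 17 and the conflict inside Section 24 do not depend on it.

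2. **Same object?** Section 18.1 speaks of results, Section 24 of unblinded data. The difference does not help, since a party holding unblinded data can compute the results.

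3. **Same period?** The Section 24 sentence covers the time during which the trial evolves. Section 17 sets no end to sponsor blinding, and Section 18.1 runs it to the end of the study. The periods overlap.

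4. **Does the preceding sentence limit it?** The code restriction excludes the Sponsor until exposure is complete. The next sentence grants the Sponsor access without repeating that limit.

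5. **Does the procedures sentence cure it?** No. It addresses needless unblinding of individuals and combined ongoing results. It neither withdraws the access nor says what the procedures are.

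6. **Does notice of graduation explain it?** No. Section 5 has the sponsor or responsible party told when an intervention graduates. That is a decision, as in Section 18.1, not access to data.

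7. **Do the end-points agree?** There are three: completion of exposure (Section 24, code), database lock (Section 24, opening) and end of the study (Section 18.1). Section 2 places the final analysis after all participants reach the safety follow-up visit, and Section 6 defines safety follow-up separately from treatment. Exposure can therefore be complete before the database is released and the Section 8.4 classification meeting is held. The end of the study is undefined for a platform described as perpetual.

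8. **Is the rest of Section 24 consistent?** The opening rule blinds everyone involved in analysis until lock, with no exception for the CRO and the IDMC, which the next paragraph allows to see the code. Removing the Sponsor from one sentence would not resolve that.

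**The case against.** The strongest defence is that the sentence lacks a qualifier and was never meant to open live interim data. The terminology table in Section 2 reserves the word trial, at the top level, for the whole platform. ISTs end at different times, and the code restriction lifts intervention by intervention. On that usage, access as the trial evolves could mean access to each IST once it has finished while the platform continues. This is plausible and may be what was intended, but the sentence does not say so. Step 7 also shows that completion of exposure would be too early a trigger. The defence therefore supports a clarification and does not remove the defect.

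A second defence is that the trial was not initiated and the SAP calls itself unfinished. That lowers the practical stakes: the documents give no ground for saying that anyone was improperly unblinded. But Sections 17, 18.1 and 24 are not among those marked unfinished. The precedence rule in Section 2 settles conflicts between the Master SAP and an ISA, not conflicts within the Master SAP.

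Some stronger inferences are tempting and do not stand:

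- **A count of exposed looks.** Looks are quarterly, but the ISA sets an IST's duration. They start only when 50 participants have 12 months of follow-up (the default). Assuming instant enrolment and a 48- or 60-month course, the most possible is (48 − 12)/3 + 1 = 13 or (60 − 12)/3 + 1 = 17. Neither course length is given as an IST duration, and the finding needs no count.
- **Shared placebo spreads the exposure to every IST.** This does not follow. Any breadth would come from the sentence not being confined to one IST. The SAP also has cross-IST safeguards: limits on calculations with unblinded active data from several ISTs (Sections 2 and 8.4), on listings (Section 9.1) and on reports (Section 24). None of them removes Sponsor access within an IST.
- **The Sponsor could steer added endpoints or subarm changes.** Endpoint upgrades are described in the ISA and need steering-committee approval (Section 7). Subarm rules are detailed in the ISA (Section 5). The documents do not show that these choices stay open to the Sponsor.
- **The DSMB is locked out.** Section 24 restricts the code. Section 17 gives the DSMB unblinded assessment, which can rest on output the CRO prepares. Leaving the DSMB out of the code list is not a contradiction.

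**Conclusion.** The inconsistency is real and should be corrected before the SAP is reused. Section 24 gives the Sponsor access to unblinded data during the trial without limiting it to completed ISTs. Section 17, Section 18.1 and the preceding sentence of Section 24 say otherwise, and no firewall procedure could comply with all of them as worded.

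The finding has no numerical size. Its consequence is that two steps meant to be blind, analysis-set classification and the all-controls cut-off, could be preceded by Sponsor unblinding. The documents do not say that the Sponsor takes those steps, so influence is possible but not demonstrated. The conclusion assumes that Sponsor means the same party in Sections 17 and 24, which the wording supports. It does not assume that live access was intended.

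**What to change.** 1. In Section 24, remove the Sponsor from the subject of the access sentence, leaving the External Statistical CRO. If access after completion was meant, limit it explicitly to ISTs that have completed and been locked.
2. Amend the procedures sentence that follows to match.
3. State that during an ongoing IST only three parties see unblinded data: the CRO's unblinded team, the IDMC (efficacy) and the DSMB (safety output, as in Section 17). Except them from the blanket rule that opens Section 24.
4. Replace the three end-points with one for sponsor blinding, used in Sections 17, 18.1 and 24. Define it at IST level because the platform is perpetual, and place it after database lock, once the classification meeting has been held and the all-controls cut-off fixed.

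The cost is wording in these sections, carried into the IDMC and DSMB charters. No participant procedure, sample size or analysis changes.

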Annex I. SAS code for simplified frequentist version of primary analysis

The SAS code below covers a simplified frequentist version of the model.

It includes two strata, referenced as 1 and 2 as well as a and b. Time points included are baseline (0) and 6, 12, 18 and 24 months. The dataset should include one record for each visit for each participant. Research participants are identified by rpid.

Parameters α are denoted, for example, as meana6. Parameter μ is denoted mean0. The variance of γ is the parameter s2pt. The parameter σ (the variance of ϵ) is denoted s2e.

```
proc nlmixed data=rbansdata;

parms mean0=100 meana6=-5 meanb6=-2 meana12=-8 meanb12=-3 meana18=-11 meanb18=-4 meana24=-14 meanb24=-5
cprrr=1 s2e=25 s2pt=100;

if (stratum=1) then
change=((time=6)*meana6)+((time=12)*meana12)+((time=18)*meana18)+((time=24)*meana24);

if (stratum=2) then
change=((time=6)*meanb6)+((time=12)*meanb12)+((time=18)*meanb18)+((time=24)*meanb24);

mean=mean0+((treat=0)*change)+((treat=1)*cprrr*change)+pt;

random pt ~ normal(0,s2pt) subject=rpidd;

model rbans ~ normal(mean,s2e);

estimate 'logcprrr ' log(cprrr);

ods output fitstatistics=fit;

ods output parameterestimates=est;

ods output convergencestatus=status;

ods output additional estimates=addest;
```
